4.4 Early Withdrawal of Subjects

4.4.1 When and How to Withdraw Subjects

- Subjects decision to withdraw from the study (withdrawal of consent)
- Failure of subject to adhere to protocol requirements (missing more than two infusions within the first 8 weeks or more than three infusions in the following 4 months). If a patient experiences an adverse event and the PI determines the next dose must be delayed, the dose may be delayed for up to 4 weeks and continue on the protocol schedule without being withdrawn.
- Disease progression (> 50% increase in proteinuria and > 30% reduction in GFR as measured by creatinine clearance) at day 77 visit
- Severe infection (defined as the development of pneumonia, severe urinary tract infection/pyelonephritis, sepsis, meningitis)
- If Hgb < 8.0 g/dL or platelet < 50,000, or WBC < 3.0 or absolute neutrophil count (ANC) < 500, the infusion will be held and restarted once blood counts have improved.

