4.4.2 Data Collection and Follow-up for Withdrawn Subjects

- Subjects that withdraw consent or are withdrawn from the study due to safety issues or not following through with the protocol will be followed clinically by the PI or co-investigators or will be sent back to the referring nephrologist

5 Study Drug

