5.5 Subject Compliance Monitoring

This drug is administered intravenously in the CRU and we can ensure compliance. If patient misses more than one infusion within the first 8 weeks or more than two infusions in the following 4 months the subject will be withdrawn from the study. We will continue to follow the subject as part of the research study with blood and urine studies and clinic visits to ensure safety.

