5.6 Prior and Concomitant Therapy

The patient should be off of all immunosuppressive therapies (cyclophosphamide, MMF, cyclosporine, tacrolimus, azathioprine, ACTH) within three months of enrollment in the study. If patient has received rituximab prior to the study there should be evidence of B-cell reconstitution prior to enrollment (CD 20 count >5). The subject should be off of prednisone or glucocorticoid equivalent in the last 6 weeks prior to enrollment, unless they are being treated with low dose oral prednisone or glucocorticoid for a condition unrelated to PGNMID or C3GN (e.g., asthma, gout) at a daily dose of 10mg or less.

Patients can receive ACE-I or ARB while enrolled in the study but dose adjustment is not allowed unless down titration for safety reasons.

Rescue treatment is not permitted while receiving daratumumab. If patient is failing treatment with evidence of disease progression (> 50% increase in proteinuria and > 30% reduction in GFR based on creatinine clearance) on visit day 77, the subject will be withdrawn from the study and can then receive other immunosuppressive therapy per discretion of the treating physician.

Management of Hepatitis B Virus Reactivation

Primary antiviral prophylaxis is permitted as per local standard of care. Per protocol, HBV DNA testing by PCR is mandatory for subjects at risk for HBV reactivation see Section 6.

For subjects who are diagnosed with HBV reactivation while on treatment, study treatment should be interrupted until the infection is adequately controlled. If the benefits outweigh the risks, study treatment may be resumed with concomitant antiviral prophylaxis as per local standard of care. Consult a liver disease specialist as clinically indicated.

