7.2 Statistical Methods

Descriptive Statistics

Univariate descriptive statistics and frequency distributions will be calculated, as appropriate for all variables. Baseline values for demographic, clinical, and outcome variables (primary and secondary) in each response category will be tabulated. Time-to-response will be analyzed descriptively with Kaplan-Meier method.

For the primary endpoint, the number and proportion of patients with treatment-emergent major infections, grade 3 or 4 anemia, leukopenia or thrombocytopenia will be summarized. Changes in Hgb, WBC count and platelet count from baseline (Day 0) will be analyzed through a paired t-test by comparing post-baseline to baseline values. The secondary endpoint of the proportion of patients with complete or partial response will be summarized in a similar manner.

It is expected that 9 patients will enter the OLE. The rate of relapse in addition to the time to relapse from the last dose of daratumumab to initiation of retreatment will be evaluated. Paired t-test will be used to evaluate change in the proteinuria from time of relapse to the end of the study. Rate of CR and PR will be evaluated at the end of the OLE.

Handling of Missing Data

This is a study of only 12 patients and expect that majority of patients will have complete data available.

Primary Hypothesis: Daratumumab is safe and well-tolerated in patients with PGNMID and C3GN associated with monoclonal gammopathy

To test this hypothesis, the incidence of major infection will be examined, specifically the development of pneumonia, severe urinary tract infection/pyelonephritis, sepsis, meningitis will be reported. In addition, anemia, leukopenia, thrombocytopenia will be examined by evaluating changes in Hgb, WBC count and platelet count, respectively. Statistical significance will be assessed using paired t-test comparing 6 months and 1 year value compared to baseline. The

number of patients who had to discontinue drug due to side effect (drop in blood counts, infection) will also be reported.

Secondary Hypothesis: Daratumumab is effective in inducing remission (defined as improvement in proteinuria and eGFR) in patients with PGNMID and C3GN associated with monoclonal gammopathy

A paired t-test will be performed to assess change in proteinuria and renal function at 6 months and 12 months compared to baseline (screening visit).

Interim Analysis

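### The 6- and 12-month efficacy analyses have no rule for patients withdrawn at Day 77 for progression; as written, the paired t-test loses these failures, which favours the drug

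*Combined protocol and SAP*

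**What the plan says.** **Efficacy test.** Section 7.2 (Statistical Methods, Secondary Hypothesis): "A paired t-test will be performed to assess change in proteinuria and renal function at 6 months and 12 months compared to baseline", baseline being the screening visit.

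**Withdrawal for progression.** Section 4.4.1 lists as a reason for withdrawal: "Disease progression (> 50% increase in proteinuria and > 30% reduction in GFR as measured by creatinine clearance) at day 77 visit". Section 5.6 repeats the criterion and adds that "the subject will be withdrawn from the study and can then receive other immunosuppressive therapy per discretion of the treating physician".

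**Follow-up after withdrawal.** Section 4.4.2 concerns "Subjects that withdraw consent or are withdrawn from the study due to safety issues or not following through with the protocol" and says that they "will be followed clinically by the PI or co-investigators or will be sent back to the referring nephrologist". Section 5.5, after its missed-infusion rule, says: "We will continue to follow the subject as part of the research study with blood and urine studies and clinic visits to ensure safety". Neither section names progression.

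**Missing data.** Under that heading, Section 7.2 notes that there are only 12 patients and that the investigators "expect that majority of patients will have complete data available". It gives no method.

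**Response.** Section 3.3 defines complete, partial and no response, each at 12 months. Section 7.2 adds: "The secondary endpoint of the proportion of patients with complete or partial response will be summarized in a similar manner". Time to response is to be described by Kaplan-Meier, with no censoring rule. The only analysis set, under Subject Population(s) for Analysis, is every subject who received at least one dose.

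**The concern.** The Day 77 withdrawal depends on the outcome. The two variables that trigger it, proteinuria and creatinine clearance, are the ones tested at 6 and 12 months and used to define response. A patient removed by the rule has, by definition, done badly on both.

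A paired t-test can use only patients with both values. If a progressor has no later value, the test is run on those who did not fail early, and the average change looks better than it was among all treated patients. With no control arm, nothing offsets this: the change in proteinuria and the remission rate are the main efficacy evidence. With 12 patients, one omission can matter.

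The response proportion and the time-to-response curve are exposed to a lesser degree. A patient with no 12-month value fits none of the 12-month categories as written, and the plan does not say whether the curve censors that patient at Day 77.

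**Working it through.** **1. Is there a route to 6- and 12-month research values for progressors?**

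| Section | Who is covered | What follows |
|---|---|---|
| 4.4.1, 5.6 | Progression at Day 77 | Withdrawn; other therapy allowed; no data collection stated |
| 4.4.2 | Consent, safety, non-adherence | Clinical care or return to the referring nephrologist |
| 5.5 | Missed infusions | Research blood and urine studies and clinic visits |

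No row supplies the values for progressors. Sections 4.4.2 and 5.5 also disagree with each other about non-adherent patients.

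**2. Nothing to reproduce.** Section 7.1 states that no power calculation was done. The documents give no SD, progression rate, analysis scale or efficacy alpha. Every size below therefore rests on assumptions.

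**3. Effect of one omitted progressor (illustration).** Assume 11 completers with mean proteinuria change −30% and SD 35 points, and one progressor at +50%, the lower bound of the rule.
- Progressor omitted: t = −30 / (35/√11) = −30/10.55 = −2.84, 10 df, two-sided p = 0.018.
- Progressor kept: mean = (11 × (−30) + 50)/12 = −23.3%. Sum of squares = 10 × 35² + 11 × 6.67² + 73.33² = 12,250 + 489 + 5,378 = 18,117. SD = √(18,117/11) = 40.6. t = −23.3/(40.6/√12) = −1.99, 11 df, p = 0.072.

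**4. Simulation over an assumed range.** Log changes in Day 77 proteinuria, Day 77 GFR and final proteinuria are jointly normal. A patient is removed if the Day 77 proteinuria ratio exceeds 1.5 and the GFR ratio is below 0.7. Assumed inputs:
- log-proteinuria SD 0.5, 0.7, 0.9
- log-GFR SD 0.2, 0.35
- proteinuria-GFR correlation −0.3, −0.5, −0.7
- Day 77-to-final correlation 0.7, 0.9

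This makes 3 × 2 × 3 × 2 = 36 combinations, each with 40,000 trials of 12 and a one-sided 2.5% test (assumed).

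| | No true effect | True halving |
|---|---|---|
| Patients removed, of 12 | 0.2 to 1.5 (median 0.5) | 0.02 to 0.8 |
| Completers' geometric mean ratio | 0.99 to 0.86 (median 0.96) | 0.50 to 0.45 (truth 0.50) |
| False benefit, completers | about 3 to 7% | not applicable |

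With no true effect, the chance of losing at least one patient is about 18 to 79%.

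**5. Other assumptions.** Letting mean GFR drift down (log change −0.15 to −0.3), with larger SDs (log-proteinuria 0.8, log-GFR 0.4) in some settings and no true proteinuria change, gives up to 2.7 patients removed, a completers' ratio as low as 0.80 and false benefit up to about 13%.

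**6. Scale.** With an unlogged paired t-test (assumed lognormal baseline, median 3000 mg, log SD 0.7), false benefit is 1.0 to 3.3% with progressors dropped, against 0.6 to 1.3% with complete data, when the geometric mean is unchanged. It is 6 to 24% against 5 to 12% when the arithmetic mean is unchanged. Dropping progressors raises the rate on either scale, but the level depends on a scale that the plan does not state.

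**The case against.** The strongest reply is that no sentence excludes progressors. Section 4.4.2 does not list them, so it does not send them out of research follow-up. Section 3.1 says patients are followed for 12 months, and Section 5.5 shows that research sampling after withdrawal was contemplated. This stands to the extent that the exclusion is inferred from the withdrawal rule and the test. It does not supply the missing values or a rule for their absence.

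On response, a reader might infer that the rate will be computed among completers. Section 7.2 expects 9 patients to enter the extension, which requires remission; 9/12 = 75% would then become 9/11 = 82% or 9/10 = 90% if one or two failures left the denominator. The documents do not support that reading. All treated patients are the only defined population, the no-response wording describes a progressor well apart from its timing, and the 9 is an enrolment expectation. Those fractions are illustrations only. What remains is that no rule classifies a withdrawn patient.

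It is also fair that withdrawal needs both criteria at one visit, that the median simulated loss is half a patient, and that this is a secondary endpoint in an unpowered proof-of-concept study.

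**Conclusion.** The concern holds as a gap in the analysis rules with a known direction. Progressors are withdrawn because of the tested variables, no later research values are provided for them, and the paired t-test cannot use them without such values. Whenever a progressor occurs, this is expected to favour the drug. For the response proportion, all treated patients is the reasonable denominator, but non-responder status is unstated.

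The size is not settled. A reader might infer from the medians that the bias is modest, or from the p-value example that it is decisive; the documents support neither. On the assumed log-scale inputs with no true effect, false benefit is about 3 to 7% instead of 2.5%, and up to about 13% under other assumptions. With a true halving the completers' ratio moves from 0.50 to no lower than 0.45. With no progressor there is no bias. This should be fixed before results are seen. It does not touch the primary safety endpoint.

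**What to change.** 1. **Response (Section 7.2).** State that the proportion with complete or partial response uses all treated patients, with an exact 95% CI. Count as non-responders those withdrawn, missing at month 12, or given non-protocol immunosuppression before Day 365. Keep them in the time-to-response curve as non-responders to the end of follow-up.
2. **Change in proteinuria and creatinine clearance (Section 7.2).** Keep progressors through the Day 77 value, which the withdrawal rule already requires. At minimum, report beside the paired t-test an analysis that carries forward the last value before withdrawal or other therapy. In the log-scale check for proteinuria with no true effect, this gave a ratio of about 1.00 to 1.05 and false benefit of 1.8 to 2.6%. A repeated-measures model is an acceptable alternative. State the analysis scale.
3. **Follow-up (Sections 4.4.2 and 5.5).** Reconcile the two statements on research follow-up of withdrawn patients, and say whether the result applies to progressors.

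**Cost.** Items 1 and 2 are SAP wording; item 3 is one reconciled sentence. The reported response rate may be slightly lower, the carry-forward analysis has somewhat lower power if the drug works, and there is a little more analysis. If samples are collected from progressors, that is two sample sets each for about 0 to 2 patients; values after other immunosuppression would not enter the efficacy analysis.

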7.2 Subject Population(s) for Analysis

All-treated population: Any subject that received at least one dose of study drug.

8 Safety and Adverse Events

The primary side effects associated with daratumumab include anemia, neutropenia and thrombocytopenia and these will be evaluated initially by monthly CBC done on Day 21, 49, 77, 105, 133, 161 and then every 3 months done on Day 264, 365. Further, these will be evaluated during OLE laboratory assessments.

Other side effects include risk of infection specifically pneumonia and patients will be asked about any signs of symptoms suggestive of infection (e.g fever, cough) or any hospitalization, emergency department visits or other doctor visits at the clinical visits on Day 49, 77, 133, 161, 264, 365 and during OLE when laboratory assessments are completed or an infusion is administered. Other side effects include symptoms of nausea and fatigue and similarly patients will be asked regarding these symptoms at the time of clinic visits and during OLE when laboratory assessments are completed or an infusion is administered.

8.1 Definitions

Unanticipated Problems Involving Risk to Subjects or Others (UPIRTSO)

Any unanticipated problem or adverse event that meets the following three criteria:

- Serious: Serious problems or events that results in significant harm, (which may be physical, psychological, financial, social, economic, or legal) or increased risk for the subject or others (including individuals who are not research subjects). These include: (1) death; (2) life threatening adverse experience; (3) hospitalization - inpatient, new, or prolonged; (4) disability/incapacity - persistent or significant; (5) birth defect/anomaly; (6) breach of confidentiality and (7) other problems, events, or new information (i.e. publications, DSMB reports, interim findings, product labeling change) that in the opinion of the local investigator may adversely affect the rights, safety, or welfare of the subjects or others, or substantially compromise the research data, **AND**
- Unanticipated: (i.e. unexpected) problems or events are those that are not already described as potential risks in the protocol, consent document, not listed in the Investigator's Brochure, or not part of an underlying disease. A problem or event is

"unanticipated" when it was unforeseeable at the time of its occurrence. A problem or event is "unanticipated" when it occurs at an increased frequency or at an increased severity than expected, AND

- Related: A problem or event is "related" if it is possibly related to the research procedures.

Adverse Event

An adverse event is any untoward medical occurrence in a clinical study subject administered a medicinal (investigational or non-investigational) product. An adverse event does not necessarily have a causal relationship with the treatment. An adverse event can therefore be any unfavorable and unintended sign (including an abnormal finding), symptom, or disease temporally associated with the use of a medicinal (investigational or non- investigational) product, whether or not related to that medicinal (investigational or non-investigational) product. (Definition per International Conference on Harmonisation [ICH])

This includes any occurrence that is new in onset or aggravated in severity or frequency from the baseline condition, or abnormal results of diagnostic procedures, including laboratory test abnormalities.

Serious Adverse Event

A serious adverse event based on ICH and EU Guidelines on Pharmacovigilance for Medicinal Products for Human Use is any untoward medical occurrence that at any dose:

- Results in death
- Is life-threatening
(The subject was at risk of death at the time of the event. It does not refer to an event that hypothetically might have caused death if it were more severe.)
- Requires inpatient hospitalization or prolongation of existing hospitalization
- Results in persistent or significant disability/incapacity
- Is a congenital anomaly/birth defect
- Is a suspected transmission of any infectious agent via a medicinal product
- Is medically important*

and/or per protocol may be problems/events that in the opinion of the sponsor-investigator may have adversely affected the rights, safety, or welfare of the subjects or others, or substantially compromised the research data.

*Medical and scientific judgment should be exercised in deciding whether expedited reporting is also appropriate in other situations, such as important medical events that may not be immediately life threatening or result in death or hospitalization but may jeopardize the subject or may require intervention to prevent one of the other outcomes listed in the definition above. These should usually be considered serious.

NOTE: DEATH FOR ANY REASON SHOULD BE REPORTED AS A SERIOUS ADVERSE EVENT.

All adverse events that do not meet any of the criteria for serious, should be regarded as **non-serious adverse events**.

Adverse Event Reporting Period

For this study, the study treatment follow-up period is defined as 365 days following the last administration of study treatment.

Preexisting Condition

A preexisting condition is one that is present at the start of the study. A preexisting condition should be recorded as an adverse event if the frequency, intensity, or the character of the condition worsens during the study period.

General Physical Examination Findings

At screening, any clinically significant abnormality should be recorded as a preexisting condition. At the end of the study, any new clinically significant findings/abnormalities that meet the definition of an adverse event must also be recorded and documented as an adverse event.

Post-study Adverse Event

All unresolved adverse events should be followed by the sponsor-investigator until the events are resolved, the subject is lost to follow-up, or the adverse event is otherwise explained. At the last scheduled visit, the sponsor-investigator should instruct each subject to report, to the sponsor-investigator, any subsequent event(s) that the subject, or the subject's personal physician, believes might reasonably be related to participation in this study.

Abnormal Laboratory Values

A clinical laboratory abnormality should be documented as an adverse event if:

- Monthly CBC shows that Hgb is < 8.0 g/dL
- Monthly CBC shows that WBC is < 3.0
- Monthly CBC shows ANC < 500
- Monthly CBC shows that platelet count is < 50,000

Hospitalization, Prolonged Hospitalization or Surgery

For reports of hospitalization, it is the sign, symptom or diagnosis which led to the hospitalization that is the serious event for which details must be provided.

Any event requiring hospitalization or prolongation of hospitalization that occurs during the study must be reported as a serious adverse event, except hospitalizations for the following:

- Hospitalizations not intended to treat an acute illness or adverse event (e.g., social reasons such as pending placement in long-term care facility)
- Surgery or procedure planned before entry into the study. [Note: Hospitalizations that were planned before the start of data collection and where the underlying condition for which the hospitalization was planned has not worsened will not be considered serious adverse events. Any adverse event that results in a prolongation of the originally planned hospitalization is to be reported as a new serious adverse event.]
- [For convenience the investigator may choose to hospitalize the subject for the duration of the treatment period.]

8.2 Recording of Adverse Events

At each contact with the subject, the study team must seek information on adverse events by specific questioning and, as appropriate, by examination. Information on all adverse events should be recorded immediately in the source document, and also in the appropriate adverse event section of the case report form (CRF). All clearly related signs, symptoms, and abnormal diagnostic, laboratory or procedure results should be recorded in the source document.

All adverse events occurring during the study period must be recorded. The clinical course of each event should be followed until resolution, stabilization, or until it has been ultimately determined that the study treatment or participation is not the probable cause. Serious adverse events that are still ongoing at the end of the study period must be followed up, to determine the final outcome. Any serious adverse event that occurs after the study period and is considered to be at least possibly related to the study treatment or study participation should be recorded and reported immediately.

